9.1.4.4. Early Withdrawal – Early Exit Visit

In the event of early withdrawal from the study (ie, before Week 52), an exit visit will be conducted as soon as possible. The following procedures will be performed: an abbreviated physical examination, vital signs measurement, healthcare provider-collected cervical sample, and self-collected cervico-vaginal sample for type-specific HPV16 and HPV18 PCR, an HSV-2 serology test, recording of concomitant medications and any AEs, and collection of samples for immunogenicity assessments.

9.2. Study Evaluations

9.2.1. Safety

An IDMC will be commissioned to evaluate safety data over the course of the study and to review any events that meet a specific study pausing or stopping rule or any other safety issue that may arise. Details regarding the IDMC are provided in Section [11.8](#).

Any clinically relevant changes occurring from the signing of the ICF until 28 days after the first vaccination and from the second vaccination through the following 28 days must be recorded on the AE section of the eCRF. Outside these periods, reporting will be limited to all SAEs.

Any clinically significant abnormalities (including those persisting at the end of the study/early exit) will be followed by the investigator until resolution or until a clinically stable endpoint is reached. All AEs and laboratory data will be coded for severity according to the criteria presented in Section [12.1.3](#) (see [Attachment 2](#)).

The PI, together with the sponsor's SRP, will be responsible for the safety monitoring of the study, and will halt vaccination of further subjects in case any of the pre-specified pausing or stopping rules described in Section [11.9](#) have been met.

The study will include the following evaluations of safety and reactogenicity according to the time points provided in the [Time and Events Schedule](#):

Adverse Events

All AEs will be reported as specified in Section 12.

For solicited AEs, the following applies.

Solicited Adverse Events

After each vaccination, participants will remain under observation at the study site for at least 30 minutes for presence of any acute reactions and solicited events. In addition, participants will record solicited symptoms in a diary for 7 days post-vaccination. All participants will be provided with a diary and instructions on how to complete the Diary (Section 9.1.1). Diary information will be transcribed by the study personnel in the diary eCRF pages. Once a solicited symptom from a diary is considered to be of severity Grade 1 or above, it will be referred to as a solicited AE.

Solicited Injection Site (Local) Adverse Events

Participants will be asked to note in the diary occurrences of pain/tenderness, erythema and induration/swelling at the study vaccine injection site daily for 7 days post-vaccination (day of vaccination and the subsequent 7 days). The extent (largest diameter) of any erythema, and induration/swelling should be measured (using the ruler supplied) and recorded daily.

- **Injection Site Pain/Tenderness**

Injection site pain (eg, stinging, burning) is an unpleasant sensory and emotional experience associated with actual or potential tissue damage and occurring at the immunization site (with or without involvement of surrounding tissue). Injection site tenderness is a painful sensation localized at the injection site upon palpation or movement of the limb. Due to subjective nature of the reaction, the severity assessment of pain/tenderness is self-reported (if a participant is unable to provide self-report, other reporters include parent/care giver or health care provider).²²

- **Injection Site Erythema**

Injection site erythema is a redness of the skin caused by dilatation and congestion of the capillaries localized at the injection site. It can best be described by looking and measuring.

- **Injection Site Swelling/Induration**

Injection site swelling is a visible enlargement of an injected limb. It may be either soft (typically) or firm (less typical). Injection site induration is a palpable thickening, firmness, or hardening of soft tissue, usually has well-demarcated palpable borders, can be visible (raised or sunken compared to surrounding skin), is often ‘woody’ to touch and has a flat shape. As differentiation between swelling and induration may be difficult without health care professional’s assessment, both symptoms have been combined to allow self-assessment by the participants. Both swelling and induration can best be described by looking and measuring.

Note: any other injection site events not meeting the above case definitions should be reported separately as unsolicited AEs.^{32,33}

Solicited Systemic Adverse Events

Participants will be instructed on how to record daily temperature using a thermometer provided for home use. Participants should record the oral body temperature in the diary in the evening of the day of vaccination, and then daily for the next 7 days approximately at the same time each day (preferably in the evening). If more than one measurement is made on any given day, the highest temperature of that day will be used in the eCRF. Temperatures to be taken 7 days after the vaccination at the end of the diary period, may be collected earlier to coincide with the clinic visit.

Fever is defined as endogenous elevation of body temperature $\geq 38^{\circ}\text{ C}$, as recorded in at least one measurement.³⁶

Participants will also be instructed on how to note daily in the diary symptoms for 7 days post-vaccination (day of vaccination and the subsequent 7 days) of the following events: fatigue, headache, nausea, myalgia, arthralgia, and chills.

Unsolicited Adverse Events

The investigator or study-site staff will document any reported unsolicited AEs and perform causality evaluations from the time of ICF signature through 28 days after the first vaccination, and from the time of the second vaccination until 28 days afterwards. SAEs will be collected from the time of ICF signature until the study end.

Laboratory Safety Assessments

Blood samples will be collected for safety laboratory assessments (hematology and biochemistry) as follows on all participants:

- At screening^a
- At 7 days post-Dose 1 and post-Dose 2

The following tests will be performed by a central laboratory:

- **Hematology Panel**

Hemoglobin

White blood cell count with differential

Platelet count

Prothrombin time^b

Activated partial thromboplastin time^b

^a Clinical laboratory tests will be collected on all participants screened for this study.

^b Parameters only measured at screening

- **Biochemistry Panel**

Sodium
Potassium
Creatinine
Blood urea nitrogen
Aspartate aminotransferase
Alanine aminotransferase

Review and Grading of Laboratory Data

The investigator must review the laboratory results, document this review, and record any clinically relevant changes occurring during the study in the AE section of the eCRF. Laboratory reports must be filed with the source documents.

Laboratory values will be initially evaluated by the investigator according to central laboratory criteria. Abnormal values outside the central laboratory range of normal will be graded according to the toxicity tables from the FDA Guidance document “Toxicity Grading Scale from Healthy Adult and Adolescent Volunteers Enrolled in Preventive Vaccine Clinical Trials” (see [Attachment 2](#)). Laboratory values within central laboratory normal limits will not be FDA graded and will be considered as normal.

Any clinically significant abnormal laboratory value occurring during the 28-day follow-up after each vaccination will be captured as an AE. For clinically significant abnormal laboratory values, the test must be repeated within a reasonable period of the site becoming aware of the abnormal value.

Additional Clinical Laboratory Assessments

Additional clinical laboratory assessments will be performed:

- Serum pregnancy testing (β -hCG) for women of childbearing potential at screening
- Urine pregnancy testing for women of childbearing potential on the day of each vaccination (pre-vaccination)
- Serology testing (HIV type 1 or type 2, hepatitis B, hepatitis C) at screening
- Serology testing (HSV-2) on the day of the first vaccination and the 12-month follow-up visit (or the early exit visit, if applicable).

Vital Signs

Vital sign measurements will be performed at time points specified in the [Time and Events Schedule](#). Supine blood pressure and pulse/heart rate measurements should be preceded by at least 5 minutes of rest in a quiet setting without distractions (eg, television, cell phones).

The following measurements will be performed:

- Heart rate (beats per minute), systolic blood pressure (mmHg) and diastolic blood pressure (mmHg). Confirmatory vital signs measurement can be performed if inconsistent with a prior measurement
- Body temperature (preferably orally)

If any clinically significant changes in vital signs are noted, they will be reported as AEs and followed to resolution, or until reaching a clinically stable endpoint.

Physical Examination

Full physical examination, including height and weight, will be carried out at screening. At all other visits, an abbreviated, symptom-directed examination will be performed by the investigator based on any clinically relevant issues, clinically relevant symptoms and medical history. Symptom-directed physical examination may be repeated if deemed necessary by the investigator.

Physical examinations will be performed by the investigator or designated medically trained clinician. Any abnormalities or changes in severity noted during the review of body systems should be documented in the source document and recorded in the eCRF.

9.2.2. Immunogenicity

Venous blood samples will be collected for the determination of humoral and cellular responses, according to the [Time and Events Schedule](#). Sample collection and processing will be performed by the staff at the clinical site according to current versions of the approved clinical site's standard procedures.

Since the vaccine targets a cellular therapeutic response, the emphasis will be on the assessment of cellular immune responses. During the study, cellular immune responses will be measured in all participants at 5 time points during the 12-month follow-up period after the first vaccination:

- pre-Dose 1, pre-Dose 2, at 21 days, 6 months post-Dose 2 and 12 months post-Dose 1

Cellular immunological assays are summarized in [Table 5](#). Humoral immunological assays are summarized in [Table 6](#). Exploratory analyses may be performed, including, but not limited to, the listed assays. Baseline and post-vaccination samples will be used for the characterization of immunological assays.

Table 5: Summary of Immunogenicity Assays (Cellular)

Assay	Purpose
Secondary endpoints	
ICS	Analysis of T cell responses to the separate or combined protein peptide pools of HPV16 and HPV18 E2, E6 and E7 proteins, including specific CD4 ⁺ and CD8 ⁺ T cells producing IFN γ , TNF α , or IL-2 (combined cytokine expression may also be assessed)
Exploratory endpoints	
ICS	Analysis of other cellular responses to the separate or combined protein peptide pools of HPV16 and HPV18 E2, E6 and E7 proteins (including, but not limited to, mucosa-homing markers, Th17, Th2, Treg, cytolytic markers, activation markers, exhaustion markers)
Transcriptome analysis	Analysis of gene expression patterns to provide phenotypic and functional characterization of PBMCs ex vivo or after stimulation with HPV16 and/or HPV18 E2, E6, and/or E7 peptide pools.
ELISpot responses	Enumeration of IFN γ -producing HPV16 and/or HPV18 E2 (complete, N-terminal, and/or C-terminal peptide pools), E6 and/or E7-specific T cells
ChipCytometry	Analysis of T cell responses to the separate or combined protein peptide pools of HPV16 and/or HPV18 E2, E6, and E7 proteins in PBMCs, including but not limited to CD4 ⁺ and CD8 ⁺ T cells producing IFN γ , TNF α and/or IL-2

ELISpot=enzyme-linked immunospot; HPV=human papillomavirus; ICS=intracellular cytokine staining; IFN=interferon; IL=interleukin; NK=natural killer; PBMC=peripheral blood mononuclear cell; Th=T-helper (cell); TNF=tumor necrosis factor; Treg=regulatory T cell

Table 6: Summary of Immunogenicity Assays (Humoral)

Assay	Purpose
Exploratory endpoints	
Adenovirus neutralization assay	Analysis of neutralizing antibodies to adenovirus vector
MVA neutralization assay	Analysis of neutralizing antibodies to MVA vector
L1/L2 ELISA	Analysis of L1 and/or L2 antibodies by ELISA to HPV16 and/or HPV18 or other HPV genotypes
E2, E6 and E7 ELISA	Analysis of E2, E6 and/or E7 antibodies to HPV16 and/or HPV18 or other HR-HPV genotypes

ELISA=enzyme-linked immunosorbent assay; HPV=human papillomavirus; HR-HPV=high-risk human papillomavirus; MVA=modified vaccinia Ankara

Sample collection and processing will be performed by study-site personnel according to current versions of approved SOPs.

9.2.3. Virology and Histology

HPV16 and HPV18 genotyping will be performed with a qualitative PCR test (Cobas[®], Roche) on the cervical samples. Prior to vaccination, a participant will have a confirmed diagnosis of an HPV16 or HPV18 infection. More information on the identification of an HPV infection is provided in the flow chart (Figure 4).

Cervical samples will be collected by the healthcare provider and by the participant (self-sampling) at the time points indicated in the [Time and Events Schedule](#). Healthcare provider-obtained cervical samples collected using an endocervical brush will be processed in a transport medium and send to the central laboratory. Participants will self-collect cervico-vaginal samples with a dry self-sampling device (Evalyn[®] Brush, Rovers Medical Devices) at the study site. Immediately after collection of the cervico-vaginal specimen for this study, the Evalyn[®]

Brush should be dispensed in ThinPrep® following the procedure described in the Laboratory Manual. After collection of the cervico-vaginal sample, the dry Evalyn® Brush will be suspended in transport medium at the study site and sent to the central laboratory.

Cobas® testing will be performed by a central sponsor designated laboratory.

A quantitative HPV PCR genotyping test that detects HPV16 and HPV18 together with other individual HR-HPV types will be used on all cervical samples (healthcare provider-collected and self-collected) to address the exploratory endpoints.

Colposcopy examination will occur during screening only for those participants who do not have recent (within the last 12 months) examination results. A mandatory colposcopy examination will occur 12 months after the first dose for all participants. All colposcopy biopsy specimens will be sent to a central laboratory for standardized interpretation. Histopathological reports on biopsy and excision specimens will classify findings as: negative, CIN1, CIN2, CIN3, AIS and invasive malignancy. Note: All participants will have HSV-2 serology testing on the day of the first vaccination and the 12-month follow-up visit (or the early exit visit, if applicable).

Should a participant have an examination or treatment with a non-study gynecologist, she will be asked if she consents to allow study staff to access her medical records and obtain slide and tissue for evaluation.

Management and medical follow-up after the mandatory colposcopy evaluation will be at the discretion of the investigator and local guidelines.

Participants who discontinue the study will be recommended to continue regular cervical cancer screening.

10. PARTICIPANT COMPLETION/DISCONTINUATION OF STUDY VACCINE/ WITHDRAWAL FROM THE STUDY

10.1. Completion

A participant will be considered to have completed study vaccination if she has received all study vaccinations. A participant will be considered to have completed the study if she has completed assessments through to the end of the study (ie, Day 366) even if she did not receive the second vaccination.

10.2. Discontinuation of Study Vaccine/Withdrawal from the Study

Discontinuation of Study Vaccine

Participants will discontinue further study vaccine administration for the reasons listed below. These participants must not receive any additional dose of study vaccine but should be followed-up until the end of the follow-up period at Week 52 (12 months post-Dose 1 visit) with assessments of safety, immunogenicity and virology. Additional unscheduled visits may be

performed for safety/reactogenicity reasons, if needed. In case of questions, the investigator is encouraged to contact the sponsor.

- Any related AE, worsening of health status or intercurrent illnesses that, in the opinion of the investigator, required discontinuation from study vaccine
- The participant becomes pregnant
- Unblinding on the participant level that, in the opinion of the sponsor, would compromise the integrity of the data
- Anaphylactic reaction following vaccination
- SAE or other potentially life-threatening (Grade 4) event that is determined to be related to study vaccine
- Chronic or recurrent use of immunosuppressants (after discussion with the sponsor)
- Missing a study vaccination

Withdrawal From the Study

Each participant has the right to withdraw from the study at any time for any reason. The investigator should make an attempt to contact participants who did not return for scheduled visits or follow-up. Although the participant is not obliged to give reason(s) for withdrawing prematurely, the investigator should make a reasonable effort to ascertain the reason(s) while fully respecting the participant's rights.

A participant will be withdrawn from the study for any of the following reasons:

- Lost to follow-up
- Withdrawal of consent
- Death
- Repeated failure to comply with protocol requirements
- Decision by the sponsor or the investigator to stop or cancel the study
- Decision by local regulatory authorities or Institutional Review Board/Independent Ethics Committee (IRB/IEC) to stop or cancel the study

If a participant is lost to follow-up, every reasonable effort must be made by the study-site personnel to contact the participant and determine the reason for discontinuation/withdrawal. The measures taken to follow-up must be documented.

When a participant withdraws before completing the study, the reason for withdrawal is to be documented in the eCRF and in the source document. Study vaccine assigned to the withdrawn participant may not be assigned to another participant. In general, participants who withdraw will be replaced, as long as the participant has not been vaccinated yet. However, any randomized participant withdrawn from the study for reasons other than due to an AE after the first dose but

before the last dose might be replaced at the discretion of the sponsor. If a participant withdraws early from the study, assessments for early withdrawal should be obtained (see Section [9.1.4.4](#)).

Participants who wish to withdraw consent from participation in the study will be offered a single Exit visit (see Section [9.1.4.4](#)) for safety follow-up (prior to formal withdrawal of consent). They have the right to refuse.

Withdrawal From the Use of Samples in Future Research

The participant may withdraw consent for use of samples for future research (refer to Section [16.2.5](#)). In such a case, samples will be destroyed after they are no longer needed for the clinical study. Details of the sample retention for research are presented in the main ICF.

10.3. Contraindications to Vaccination

The following events constitute a temporary contraindication to study vaccination. If any of these events occur at the scheduled time for vaccination, the participant may be vaccinated up to 10 days beyond the scheduled vaccination:

- Acute illness at the time of vaccination. This does not include minor illnesses, such as diarrhea or mild upper-respiratory tract infection.
- Fever (body temperature $\geq 38.0^{\circ}\text{C}$) at the planned time of vaccination.

If the vaccination visit cannot be rescheduled within the allowed window or the contraindications to vaccination persist, the sponsor should be contacted for further guidance.

11. STATISTICAL METHODS

Statistical analysis will be done by the sponsor or under the authority of the sponsor. A general description of the statistical methods to be used to analyze the safety, immunogenicity and virology data is outlined below. Specific details will be provided in the statistical analysis plan (SAP).

Planned analyses are described in Section [11.7](#).

11.1. Analysis Sets

Vaccination assignment will follow the as treated principle.

11.1.1. Full Analysis Set

The Full Analysis Set (FAS) will include all participants with at least 1 vaccination.

11.1.2. Per-Protocol Immunogenicity Population

The Per-Protocol Immunogenicity (PPI) population will include all randomized and vaccinated participants for whom immunogenicity data are available excluding participants with major protocol deviations expecting to impact the immunogenicity outcomes. In addition, if participants miss the second dose, but continue the planned visit schedule, samples taken after the planned but missed dose will not be taken into account.

11.2. Sample Size Determination

While mild to moderate local and systemic AEs are expected, AEs that preclude further vaccination or more serious ones that would limit product development are not anticipated. With 20 participants in 1 vaccine regimen, the observation of 0 such reactions after the first vaccination would be associated with a 95% confidence that the true rate is less than 13.9%. Across regimens (n=48), the observation of 0 such reactions after the first vaccination would be associated with a 95% confidence that the true rate is less than 6.1%.

11.3. Participant Information

For all participants, demographic characteristics (eg, age, height, weight, body mass index, and race), and other baseline characteristics (eg, physical examination, medical history, and concomitant diseases) will be tabulated and summarized with descriptive statistics.

Baseline characteristics will include HPV infection history as well as HPV infection type, the latter being categorized as follows:

- Participants with persistent infection defined as at least 2 positive cervical HPV PCR tests with an interval of at least 11 months as follows: 2 positive HPV16 (or 2 positive HPV18 tests) or, if the genotype of the first test is unknown and after consultation with the sponsor, HR-HPV positivity followed by HPV16 (or HPV18) positivity. Note: the historical positive cervical HPV PCR test will be taken into account for the definition regardless of the length of the interval (>11 months) as long as there were no known negative results in between.
- Participants with recently diagnosed (within 12 months prior to baseline) HPV infection which is not persistent as defined above.

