1.1. Background

HPV Infection and Disease Burden

Among the more than 150 known HPV types, 40 are sexually transmitted and, of these, about 13 are known to be oncogenic or high-risk (HR)-HPV types.⁵³ Genital HPV infection is the most common sexually transmitted infection; most sexually active men and women acquire HPV at some point in their lives. In a national health and nutrition survey in the United States (US) covering the period 2011-2014, the prevalence of any HPV infection was 26.1% among females 14-19 years of age, increasing to 59.8% among females 20-24 years of age.²⁶ HR-HPV types are the cause of almost all cervical cancers⁵³ and a large proportion of other anogenital cancers. Around 90% of cervical HPV infections are cleared within 5 to 7 years⁴²; however, in a minority of infected women (~1%), HPV may ultimately give rise to genital neoplastic lesions. Cervical cancer led to approximately 266,000 deaths worldwide in 2012, with the biggest burden of the disease in low-income countries.⁵⁵ Among the HR-HPVs, HPV16 and HPV18 are the most

prevalent types in both low-grade and advanced disease.²⁴ HR-HPV types 16 and 18 have been established to be the underlying causative agents of more than 50% of cervical pre-cancerous lesions, and more than 70% of cervical cancer cases worldwide.^{13,20}

The 3 prophylactic HPV vaccines that are currently on the market, bivalent Cervarix® (directed against HR-HPV16 and 18), tetravalent Gardasil® (directed against HPV6 and 11, and HR-HPV16 and 18) and nonavalent Gardasil® (directed against HPV6 and 11, and HR-HPV16, 18, 31, 33, 45, 52 and 58), prevent infection through the induction of neutralizing antibodies against the major capsid protein L1.²⁹ However, the prophylactic vaccines suffer from some drawbacks: firstly, they have no therapeutic effect on established HPV-induced genital lesions.^{19,21,26,27,28,51} Secondly, the vaccine uptake is well below expectations: in 2013 in the US, only 38% of females 13-17 years of age who were eligible for prophylactic HPV vaccination completed the 3-dose course of therapy, suggesting that many people may be entering their sexually active years without protection against these HR-HPVs.⁷ Finally, these vaccines are not indicated for people over the age of 26 years, leaving a large age group unprotected.

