4.1. Inclusion Criteria

Each potential participant must satisfy all of the following criteria to be enrolled in the study:

1. must sign an ICF indicating that she understands the purpose, procedures and potential risks and benefits of the study, and is willing to participate in the study.
2. willing and able to adhere to the prohibitions and restrictions specified in this protocol.
3. female, ≥ 18 and ≤ 60 years of age, inclusive, on the day of signing the ICF.
4. Criterion modified per Amendment 3:

4.1 must have an HPV type 16 or 18 infection of the cervix as determined by a qualitative PCR test (Cobas®, Roche) within 8 weeks prior to screening or at the time of screening. Available history of HR-HPV positivity and HPV16 or HPV18 positivity will be recorded in the CRF ([Figure 4](#)).

Note: To be eligible for screening, all participants must have at least 1 historical positive cervical HR-HPV PCR test result. If the genotype of the previous test is unknown, the participant will be screened after consultation with the sponsor.

Figure 4: Flow Chart for Identifying an HPV16 or HPV18 Infection Prior to Vaccination

5. Criterion modified per Amendment 3:

5.1 Criterion modified per Amendment 2

5.2 must have a recent colposcopy result (with a maximum of 12 months old at screening); in case a colposcopy has not been performed before, it will be done as screening procedure.

6. contraceptive (birth control) use by participants should be consistent with local regulations regarding the acceptable methods of contraception for those participating in clinical studies.

Before randomization, participants must be either (as defined in [Attachment 1](#)):

- a. Not of childbearing potential
- b. Of childbearing potential and practicing an acceptable effective method of contraception and agree to remain on such a method of contraception from signing the ICF until 3 months after the last dose of study vaccine. Use of hormonal contraception should start at least 28 days before the first administration of study vaccine. Acceptable methods for this study include:
 - Hormonal contraception;
 - Intrauterine device;
 - Intrauterine hormone-releasing system;
 - Male or female condom with or without spermicide;
 - Cap, diaphragm or sponge with a vaginal spermicide;
 - Vasectomized partner (the vasectomized partner should be the sole partner for that participant);
 - Sexual abstinence*

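### Section 11.3 lets an untyped high-risk HPV result count as the first of two positives, so some newly acquired HPV16 or HPV18 infections can be placed in the persistent stratum

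*Protocol*

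**What the plan says.** Section 11.3 defines persistent infection as "at least 2 positive cervical HPV PCR tests with an interval of at least 11 months" and gives two ways to meet it. The first is type-specific: "2 positive HPV16 (or 2 positive HPV18 tests"). The second applies when the earlier result was not genotyped: "if the genotype of the first test is unknown and after consultation with the sponsor, HR-HPV positivity followed by HPV16 (or HPV18) positivity". An older positive counts "regardless of the length of the interval (>11 months) as long as there were no known negative results in between". The other category, recently diagnosed, covers infections found in the 12 months before baseline, "which is not persistent as defined above".

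Section 4.1 (criterion 4.1) requires every woman to have at least one earlier positive high-risk HPV test. It allows screening with an unknown genotype once the sponsor has been consulted, and adds: "Available history of HR-HPV positivity and HPV16 or HPV18 positivity will be recorded in the CRF". Section 1.1 says of the sexually transmitted types that "about 13 are known to be oncogenic or high-risk (HR)-HPV types".

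Sections 11.5 and 11.6 use the persistent/recent split to describe immunogenicity and viral clearance. Section 5 stratifies randomization by HPV type only, not by infection type.

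**The concern.** Persistence of an HPV16 or HPV18 infection means that the same type is found on both occasions. An untyped high-risk positive may have been any of about 13 types, so the second route cannot separate an infection that lasted from a new one that followed a different type. Because the recent category is the complement of the persistent one, a woman misplaced by this route is also missing from the group where she belongs.

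Amendment 3 opened the study to recently diagnosed infections because the sponsor wanted to explore responses in them. If new infections clear more readily than lasting ones, mixing them would raise apparent clearance in the persistent stratum and narrow its contrast with the recent stratum. The cells are small. Section 3.1 plans 9 placebo women and 10 women in each of Regimens 2 and 3 per HPV type, so before any split by infection type one placebo woman is already 1/9 = 11 percentage points.

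**Working it through.** The protocol gives no figure on this point. Its only precision statement (Section 11.2, zero events among 20 or 48 participants) concerns adverse reactions and does not bear on it. The check is therefore a reading of the definition, followed by two illustrations on assumed inputs.

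**1. What the definition does.** Take a woman who is HPV16-positive at entry, with an earlier positive at least 11 months before and no known negative between.

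| Earlier positive test | Class under Section 11.3 | Is the HPV16 infection lasting? |
|---|---|---|
| HPV16 | Persistent | Same type shown twice |
| Known to be another type | Not persistent | Not shown |
| Untyped, in truth HPV16 | Persistent, after sponsor consultation | Same type twice, but not shown |
| Untyped, in truth another type | Persistent, after sponsor consultation | No, it is new |

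The last two rows look identical in the data. The second and fourth rows are the same clinical history but receive different classes, depending only on whether the earlier sample was genotyped. Consultation has no stated criterion and cannot supply a missing genotype. The condition on intervening negatives does not detect a change of type, because a woman can stay high-risk positive while the type changes.

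**2. Share of new infections among HPV16 women entering by this route.** None of these inputs is in the documents:
- s = share of high-risk positives that are HPV16, 20-30%
- p = probability that an HPV16 infection lasts beyond 11 months, 40-60%
- a = probability that a woman with another type acquires HPV16 in the interval, 3-10%

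Share new = (1 − s)a / [(1 − s)a + s·p]

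- Lowest (s = 0.30, p = 0.60, a = 0.03): 0.021 / (0.021 + 0.180) = 0.10
- Highest (s = 0.20, p = 0.40, a = 0.10): 0.080 / (0.080 + 0.080) = 0.50

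The range is about 10-50%. Equivalently, 50-90% of women entering by this route would be truly persistent.

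**3. Effect on the whole persistent stratum.** Let u be the share of the stratum that entered by the untyped route and m the share of those with a new infection. The misclassified fraction is f = u·m, and observed clearance is (1 − f)·c_persistent + f·c_new. The values of u, m and both clearance rates are assumed.

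- u and m each 10% to 50%: f = 0.10 × 0.10 = 1% up to 0.50 × 0.50 = 25%.
- Clearance 30% (persistent) and 50% (new): observed persistent clearance is 30.2% (f = 1%) to 35.0% (f = 25%). The contrast with recent infections falls from 20 points to between 19.8 and 15.0.
- Clearance 30% and 70%: observed persistent clearance is 30.4% to 40.0%. The contrast falls from 40 points to between 39.6 and 30.0.
- u = 0: no effect.

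**The case against.** The route is disclosed and narrow. It applies only when the genotype is unknown, needs sponsor consultation and an interval of at least 11 months, and is closed by a known negative in between. A woman known to have had another type does not qualify. The protocol does not say how many women will use it. All of this stands, and it limits the claim to possible misclassification of unknown extent.

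The consequence is also limited. Section 2.2 states that no hypothesis is tested for safety or immunogenicity. Safety is primary, immunogenicity is secondary and descriptive, and clearance is exploratory. That stands too.

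Stronger readings are tempting but not supported:

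- *The split is contaminated.* Nothing in the protocol shows that any woman will enter by this route.
- *The comparison of vaccine with placebo is biased.* The class rests on pre-vaccination tests, so the error should not depend on arm. Chance imbalance in small subgroups is possible because infection type is not a randomization stratum.
- *HPV18 is affected even more.* A figure would need an acquisition rate for HPV18. Borrowing the HPV16 rate is not justified, since Section 3.1 says HPV16 infections are more prevalent. No HPV18 figure is offered.
- *The missing upper limit on the interval is the defect.* The same-type route has no upper limit either, so separating typed from untyped histories would not cure that.
- *The definition should be replaced.* On the assumptions above, 50-90% of the HPV16 women concerned are truly persistent. Removing them outright is a trade-off, not a correction.

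A sensitivity analysis can properly be left to the statistical analysis plan, which is not at hand, so its absence from the protocol is not the point. The point is the definition that Section 11.3 itself fixes. The flow chart in Figure 4 is not shown and could not be checked.

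**Conclusion.** The point holds in a limited form. As written, Section 11.3 can place a newly acquired HPV16 or HPV18 infection in the persistent stratum, and neither sponsor consultation nor the condition on intervening negatives prevents it. The extent cannot be computed from the protocol, and it is zero if no women with an untyped first test enrol. The 10-50% range for new infections applies only to HPV16 women entering by this route and rests wholly on assumed inputs. At stratum level, the equally assumed illustration gives 1-25% misclassified. That new infections clear more readily is also an assumption, because the documents give no clearance rates by infection type. For immunogenicity no direction of effect can be stated. The primary safety objective and the analyses not split by infection type are untouched. The change is worth making because it is cheap and protects the stratum results from an ambiguity that the recorded history can expose.

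**What to change.** In Section 11.3, keep the pooled definition of persistent infection but add a flag with two levels: type-confirmed (two HPV16 or two HPV18 positives) and type-unconfirmed (genotype of the first test unknown). Tabulate the two levels separately with the baseline characteristics, so that the number of women concerned is visible. In Sections 11.5 and 11.6, add the by-infection-type summaries with persistent restricted to type-confirmed women, shown alongside those under the pooled definition.

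The cost is one derived variable, built from HPV history that Section 4.1 already sends to the CRF, and a second set of descriptive summaries. The type-confirmed subgroup will be smaller, in cells that are already small. No visit, sample, eligibility rule or randomization step changes.
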